#### 4.10.1. FACS Analysis of PBMCs

The PBMC flow cytometry analysis will include detailed surface marker expression for the following: T cells, regulatory T cells (Tregs), B cells, moncytes/macrophages, and neutrophils. T cells are defined based on expression of CD3 (present on all T cells), CD4 (helper T cells), CD8 (cytotoxic T cells) and CD56 (natural killer T cells). T cell subset analysis will include the state of the T cells: naïve (CD45RA) versus memory (CD27), and the degree of T cell activation based on CD69 and HLA-DR expression. Tregs are defined based on surface expression of CD4 and CD25 and intracellular expression of FoxP3. B cells are identified based on B cell maturation markers CD19, CD20 and CD27. Monocytes/macrophages are identified based on CD14 expression. One mechanism of action of IVIG includes down regulation of IFN-y Receptor 2 on monocytes, resulting in diminished macrophage activation. Therefore, macrophage expression of IFN- $\gamma$  R2 (CD119) will be determined. Neutrophils are defined based on CD66a and CD16b expression. B cells, macrophages and neutrophils all express the activating  $Fc-\gamma$  receptor (Fc RIII; CD16) and the inhibitory Fc-γ receptor (FcγRIIB; CD32B). IVIG has been shown to down regulate FcyRIII and increase expression of FcyRIIB resulting in inhibition of activation of these cells. Thus, FcyRIII and FcyRIIB expression levels on B cells, macrophages and neutrophils will be determined.

### 4.11. Preparation and administration of study medication

#### 4.11.1. Preparation, packaging, and labeling

IVIG that will be used in this study will be Gamunex-C® (immune globulin [human],10%), from a single lot. The IVIG will be shipped periodically to the research pharmacy at each clinical site and stored under standard conditions until used for this study. The IVIG will be labeled "For Investigational Use Only".

Other study medications (ursodeoxycholic acid and TMP-SMZ will be dispensed by the clinical site research pharmacist during this trial. At each follow-up visit, dosing will be adjusted according to the infant's weight. Changes in infant's weight and dosage will be captured in the database and will be communicated to the family by the research coordinator.

#### 4.11.2. Intravenous formulation

A standard intravenous formulation of IVIG (Gamunex- $C^{\mathbb{B}}$ ) from a single manufacturer single lot (Grifols Therapeutics, Inc.) as a liquid purified form of human immune globulin will be used for this study.

#### 4.12. Adherence to protocol and withdrawal from the study

# 4.12.1. Adherence to protocol

Every effort will be made by study personnel to ensure adherence to the protocol by study subjects and their families. This includes attempt at enrollment of all eligible patients, retention of study subjects, and initiation of data collection in a timely manner. All interactions with the study subjects and their caregivers will be performed by the same personnel utilizing supportive and positive reinforcement communication skills. Compliance with oral medications will be assessed by the site research coordinator by determining if the subject took at least 80% of their doses.

#### 4.12.2. Subject withdrawal from study

It is the right of the subject's parents, or guardians, or the primary care providers caring for each subject to withdraw the subject from the study at any time during the study. Subjects will be removed from the study for any of the following reasons:

- Withdrawal of consent.
- Patient is lost to follow-up

# 4.12.3. Discontinuation of study medication

IVIG will be discontinued, but patients will continue to be followed for the duration of this study, if:

- The investigator believes it is no longer in the best interest of the patient to remain on study medication
- There is a serious adverse event or severe adverse event (level 3, 4 or 5 AE) with evidence of attribution to the IVIG, as outlined in the Data and Safety Monitoring Plan.

Any subject who is withdrawn from the study will no longer receive IVIG and will receive standard medical care. The subject will continue to be followed per protocol even if the IVIG is discontinued, unless the family or investigator withdraws the subject completely from the study.

#### 4.12.4 Subjects receiving a Liver Transplant

If a subject receives a liver transplant prior to 360 days post-HPE, any remaining IVIG infusions will be discontinued and the subject will continue to be followed only for serious adverse events. Serious adverse events will be reported as per section 7.2 and 7.3 of the protocol.

#### 4.13. Retention of participants

Special effort will be made to keep attrition of study subjects below 20% using the following methods:

- Some of the costs associated with provision of care will be covered by this study. Thus, we expect minimal attrition due to financial constraints.
- The study coordinator will provide assistance to the parents/legal guardians of study participants, such as scheduling of appointments. Thus, we will make an effort to minimize attrition due to logistical considerations.

# 4.14. Research versus standard clinical care

An important feature of this clinical trial is that subjects will receive standard clinical care at ChiLDREN centers in addition to the care related to enrollment in the trial. As outlined in Table 4, participation in this trial will specifically require the following which may be outside of standard clinical care: 1) treatment with IVIG, 2) outpatient visit at 14 days after HPE, 3) serum concentration of electrolytes, BUN, creatinine, IgG level, and 4) research blood draws. All other outpatient visits and laboratory studies may be routinely performed as part of standard clinical care of infants with biliary atresia, as summarized in Table 4 below. All study procedures described in the protocol, regardless of whether conducted as part of standard clinical care or not, are mandatory.

Conducted by*
Т
CC
CC
CC
Т
Т
Т
CC
CC
CC
CC
Т
Т
Т

\* T=Collected or administered by this clinical Trial; CC=Collected or administered as part of standard Clinical Care.

HPE=hepatic portoenterostomy surgery

# 5. STATISTICAL ANALYSIS AND DATA MANAGEMENT

# 5.1. Summary of Study Design

This study is a multicenter prospective phase 1/2A open-label trial in which the feasibility, acceptability, tolerability and safety of IVIG therapy will be assessed post-HPE in infants with biliary atresia, preliminary efficacy (activity) will be estimated, and exploratory

July 10, 2013

mechanistic research studies will be performed. Twenty-nine subjects will be enrolled into the trial, which involves three intravenous doses of IVIG at designated intervals over the first 60 days following HPE with follow-up for 360 days after enrollment.

[figure not shown]
### 5.2. Sample size

This Phase 1/2A study is primarily sized based on the precision to estimate the feasibility, tolerability and safety of IVIG in the population of infants with biliary atresia; the sample size of 29 subjects has been calculated, with 20% loss-to-follow-up expected (resulting in 23 subjects). With this sample size, we also calculated the power to compare preliminary efficacy (activity) outcomes between the IVIG subjects in this study and a comparable population of historical controls from another ChiLDREN study.

#### 5.2.1. Feasibility, Acceptability, Tolerability and Safety

To determine the feasibility, acceptability, tolerability and safety profile of IVIG treatment after HPE for BA (Aim 1), we will determine the proportion of participants who have feasibility, acceptability, tolerability and safety problems with IVIG treatment. For convenience below, we discuss power and precision in terms of adverse events (reflecting the focus on safety), although the same considerations apply to each of feasibility, acceptability, and tolerability. We anticipate that 23-29 subjects will receive IVIG. With this number of treated subjects, we have greater than 98% power to observe at least one subject with a specific adverse event when the true event rate is 20%, 91 to 95% power to observe at least one subject with a specific adverse event when the true event rate is 10%, and 69 to 77% power to observe at least one subject with a specific adverse event when the true event rate is 5%, based on calculations from the binomial distribution.

The power to reject the null hypothesis that the proportion of subjects with either a specific adverse event or any adverse event is 40% or higher, if the true proportion is 10%, 20% or 30% and using a one-sided 10% Type I error rate is provided in Figure 4. With 23 treated subjects, there is 70% power to detect a 40% or higher proportion if the true proportion is 20%, and 79% power to detect this difference with 29 treated patients (exact one-sample binomial test, SAS 9.3). These considerations also apply to the other outcomes described in Aim 1 – feasibility, acceptability and tolerability.

**Figure 4.** Power to Detect Proportion of Outcomes  $\geq$  40%, if the True Proportion is 10%, 20%, or 30% for Various Sample Sizes and one-sided Type I error of 10%

It is important to note that the level used for the null hypothesis in these calculations (40% or higher) is arbitrary and used for purposes of illustration only. Depending on the nature of the adverse event, a much higher rate might well be acceptable if the event is relatively minor and there is clear benefit in terms of lower serum bilirubin or higher survival without liver transplantation, while a much lower rate of a very serious and unusual adverse event might be unacceptable even in the presence of higher survival without liver transplantation.

# 5.2.2. Preliminary Efficacy (Activity).

The use of concurrent placebo or active control subjects was considered for this study, however it is not feasible to treat infants in a research study with an IV placebo (normal saline) and the availability of robust patient-level data for historical controls from another ChiLDREN study were felt to justify the bias issues inherent in the use of historical controls.

Placebo subjects from the ChiLDREN START (Steroids in Biliary Atresia Randomized Trial) study will be used as a historical comparative group to compare with subjects in this study who receive IVIG. Approximately 70 subjects in START received placebo from 2006-2011, but were otherwise treated similarly to the subjects in the current trial, except they received no IVIG. It is anticipated that the START randomized double-blind study will be unblinded in early 2013. With the anticipated length of this IVIG study (24-30 months enrollment and 12 months of follow-up), we will be able to use the START placebo subjects as the comparative group.

A one-sided testing strategy was chosen given that we are only interested if IVIG improves the preliminary measures of efficacy.

Hypothesis 2a states that treatment with IVIG will improve the probability of an infant having good bile flow 90 and 180 days after HPE for BA as evidenced by total serum bilirubin concentration. The primary endpoint for this hypothesis is the proportion of subjects who survive 180 days after HPE with both their native liver and serum total bilirubin <1.5 mg/dL at 180 days after HPE. Based on the ChiLDREN PROBE prospective study, approximately 51% of BA subjects who had an HPE before 4 months of age had good bile drainage at 6 months following the HPE procedure, as determined by a serum total bilirubin level <1.5 mg/dL and survival with their native liver. We anticipate the same improvement in the placebo subjects in the ChiLDREN START study.

Assuming 20% loss-to-follow-up in the ChiLDREN START study and in this study (i.e., 23 subjects in the IVIG group and 56 subjects in the START placebo group), there is 74% power with a one-sided Type I error rate of 10% to detect a difference of 25.5% -- a 50% improvement with treatment (i.e., 76.5% in the IVIG group and 51% in the placebo group). This is based on Fisher's exact test for two proportions (SAS 9.3). The corresponding power for sample sizes of 29 and 70 in the IVIG and placebo groups (if there were no drop-outs) is 82%. Alternatively, we have 80% power to detect a difference of 28% in this outcome (79% in the IVIG group and 51% in the placebo group) with sample sizes of 23 and 56 in the IVIG and placebo groups, reflecting a possible 20% drop-out rate. The corresponding power for sample sizes of 29 and 70 in the IVIG and placebo groups, if there were no drop-outs, is 88%.

Hypothesis 2b states that treatment with IVIG will improve the probability of an infant having good bile flow 360 days after HPE for BA as evidenced by the proportion of subjects who survive 360 days after HPE with both their native liver and serum total bilirubin <1.5 mg/dL at 360 days after HPE. In the prospective PROBE study, approximately 68% of BA patients who had an HPE by 4 months of age survived to 12 months of age with their native liver and had serum bilirubin <1.5 mg/dL. We assume that a comparable proportion of placebo subjects in START will have this outcome. There is 76% to 85% power to detect a 33% relative improvement in this outcome with the anticipated sample sizes described above (ranging from 23 and 56 in the IVIG and placebo groups, respectively, when adjusting for 20% drop-out, to 29 and 70 in the IVIG and placebo groups, respectively, if there were no drop-out), based on Fisher's exact test for two proportions (SAS 9.3) and a one-sided Type I error rate of 10%. This relative

improvement corresponds to approximately 90% of the IVIG subjects having improved bile flow at 360 days after HPE, compared to an anticipated 68% in START placebo patients.

Hypothesis 3 states that survival with native liver at 360 days following HPE is improved in infants treated with IVIG compared to historical controls. Since 68% of PROBE BA patients who had their HPE by 4 months of age survived to 12 months of age with their native liver and with serum total bilirubin < 1.5 mg/dL, the power calculations for Hypothesis 2b apply identically to Hypothesis 3.

**5.2.3. Biomarkers.** There are no data to inform the precision to estimate the exploratory biomarkers studied for the first time in IVIG-treated human subjects with BA.

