# 1.2. Secondary Objectives:

# Aim 2: To obtain preliminary evidence whether IVIG therapy is associated with lower serum bilirubin concentration after HPE.

*Hypothesis 2a*: The probability of an infant having good bile drainage at 90 and 180 days after HPE (as defined by survival 90 or 180 days after HPE with both their native liver and serum total bilirubin level <1.5 mg/dL at 90 or 180 days after HPE) will be greater in infants who are treated with IVIG compared to historical controls.

*Hypothesis 2b*: The probability of an infant having good bile drainage at 360 days after HPE (as defined by survival 360 days after HPE with both their native liver and serum total bilirubin level <1.5 mg/dL at 360 days after HPE) will be greater in infants who are treated with IVIG compared to historical controls.

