#### 4.2.1. Inclusion criteria

- Infant under 120 days old with established diagnosis of BA and enrolled in the ChiLDREN prospective database study (Prospective Study of Biliary Atresia Epidemiology [PROBE])
- Standard HPE operation has been performed for BA within the previous 3 days
- Post-conception age ≥ 36 weeks at time of enrollment
- Weight at enrollment  $\geq$  2000 gm
- Written informed consent to participate in the study obtained within 3 days of completion of HPE. (Note: Families of potential study subjects may be approached prior to the HPE; however consent can only be signed after the diagnosis of BA is established at surgical exploration and after HPE is performed.)

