# 4.3.2. Secondary Outcome Measures:

- 1. Percentage of subjects who survive 90 days after HPE with both their native liver and serum total bilirubin <1.5 mg/dL at 90 days after HPE. For this study, serum total bilirubin must be measured as a total and not calculated by summing bilirubin components (such as serum indirect plus direct bilirubin or conjugated plus unconjugated bilirubin).
- 2. Percentage of subjects who survive 180 days after HPE with both their native liver and serum total bilirubin <1.5 mg/dL at 180 days after HPE. For this study, serum total bilirubin must be measured as a total and not calculated by summing bilirubin components (such as serum indirect plus direct bilirubin or conjugated plus unconjugated bilirubin).
- 3. Percentage of subjects who survive 360 days after HPE with both their native liver and serum total bilirubin concentration <1.5 mg/dL at 360 days after HPE.
- 4. Percentage of subjects who survive with their native liver at 360 days after HPE.
- Percentage and absolute number of Tregs (CD4+CD25+FoxP3+), CD3/4 T cells, CD3/8 T cells, NK cells (CD56), NK T cells (CD3/56), CD19/20 B cells, macrophages (CD14/11b), and neutrophils; plasma levels of anti-enolase antibody; and plasma cytokine levels (Th1/Th2 multiplex and IL17) prior to IVIG dose #1 and at 60, 90, 180, and 360 days after HPE.

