# 4.4.4. Administration of study drug (IVIG)

IVIG will be administered on both an inpatient and outpatient\_basis. Reported adverse events and potential risks are described in Section 7. Appropriate adjustment to the IVIG infusion rate and early termination are described in Section 6. No investigational or commercial agents or therapies other than those described below may be administered with the intent to treat the subject's biliary atresia. If a subject has an acute illness at the time that an IVIG dose is due, the subject will be stabilized medically as per local standard of care before the dose of IVIG is administered. If the 30 day post-HPE visit is missed the 60 day post-HPE dose may still be administered.

Dose and timing: All participants will receive the same dose of IVIG at the same intervals in an open-label fashion as outlined in Table 2 as long as the subject does not have any increased risk for toxicity for any IVIG infusion (see Section 7.4). The day of the HPE will be considered the day that the surgery is completed (the day that the patient leaves the operating room) and this will be called Day 0. The first dose of IVIG will be given on Day 3-5 following the surgery while the subject is still in the hospital. Consent will need to be obtained before the first IVIG infusion.

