# Aim 3: To obtain preliminary evidence whether IVIG treatment after HPE will improve survival without liver transplantation at 360 days after HPE.

**Hypothesis 3:** Survival without transplantation will be greater at 360 days after HPE in infants treated with IVIG compared to historical controls.

The proportion of subjects who have survived with their native liver at 360 days after HPE will be estimated among the IVIG treated subjects and the historical placebo controls by Kaplan-Meier methods. Time to liver transplantation or death will be calculated as the number of days from the day of HPE to the first of liver transplantation, death, or last day of follow-up without these events. Subjects will be censored if these events don't occur by the last day of study follow-up. The difference between the two Kaplan-Meier estimates will be computed and a 90% upper confidence bound will be calculated for the difference, using the pooled variance (based on each group's standard error calculated with Greenwood's formula).

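### The efficacy comparison is worded for infants who receive IVIG in some places and for all subjects in others; enrolment precedes dose 1, so a treated-only set could drop enrolled infants with a worse prognosis

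*Protocol*

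**What the plan says.** Several places describe the IVIG side by receipt of drug. Section 5.2.2 says that START placebo subjects "will be used as a historical comparative group to compare with subjects in this study who receive IVIG". In 5.3, Aim 3, native-liver survival "will be estimated among the IVIG treated subjects and the historical placebo controls by Kaplan-Meier methods". Hypotheses 2a and 2b state that good bile drainage "will be greater in infants who are treated with IVIG compared to historical controls".

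Other places carry no such restriction. The 180-day outcome in 4.3.2 is "Percentage of subjects who survive 180 days after HPE with both their native liver" and a bilirubin below the threshold. The Aim 2 analysis paragraph under the hypotheses in 5.3 also refers to subjects without qualification.

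On timing, 4.2.1 requires "Written informed consent to participate in the study obtained within 3 days of completion of HPE", and 4.4.4 requires consent before the first infusion, which falls on days 3-5. Dosing applies "as long as the subject does not have any increased risk for toxicity for any IVIG infusion". It may be put off for a clinical reason within that window, and a dose is not given if the family refuses an IV line. Section 5.1 states "Twenty-nine subjects will be enrolled into the trial", and 5.2.1 adds "We anticipate that 23-29 subjects will receive IVIG". No section says whether an enrolled infant who receives no dose counts in the efficacy comparison.

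**The concern.** Whether an infant receives IVIG is settled after enrolment, partly by clinical condition in the first days after surgery. If infants who are never dosed do worse on average, removing them raises the success rate on the IVIG side with no drug effect. Section 5.2.2 accepts the bias inherent in historical controls, but this part is not inherent. Day 0 is the day of HPE for every infant, so all enrolled infants can be counted from the same point. The comparison is meant to help decide whether a larger trial is worthwhile, and a favourable shift created by the choice of analysis set would mislead that decision. The two wordings also leave the choice open until outcomes are known.

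**Working it through.** **Inputs from the protocol.** 29 enrolled (5.1). About 70 START placebo infants, Fisher's exact test, one-sided 10%, 51% control success at 180 days and 68% at 360 days (5.2.2).

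**Assumptions, not in the protocol.** The number of enrolled infants never dosed, k, and their success rate, q. I take q from 0 to 35%, and also q equal to the overall rate.

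**Reproducing the protocol's power.** I enumerated all 2×2 tables, rejected where the one-sided hypergeometric p-value is at most 0.10, and weighted by the two binomial distributions.

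| Comparison | Sizes | Stated | Computed |
|---|---|---|---|
| 76.5% vs 51% | 23 / 56 | 74% | 74.3% |
| 76.5% vs 51% | 29 / 70 | 82% | 82.2% |
| 68% × 1.33 = 90.4% vs 68% | 23 / 56 | 76% | 76.4% |
| 68% × 1.33 = 90.4% vs 68% | 29 / 70 | 85% | 85.7% |

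The method matches the protocol's.

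**False-positive rate with no drug effect.** If the success rate in all 29 is p, the rate among those dosed is

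(29p − kq) / (29 − k).

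Example: p = 0.51, k = 2, q = 0 gives 14.79 / 27 = 54.8%. With q = 0.35 it is (14.79 − 0.70) / 27 = 52.2%. Each is tested with 29 − k infants against 70 controls at p.

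| p | k | q = 0 | q = 35% | q = p |
|---|---|---|---|---|
| 51% | 0 | 6.7% | 6.7% | 6.7% |
| 51% | 1 | 9.1% | 7.4% | 6.7% |
| 51% | 2 | 12.4% | 8.3% | 6.9% |
| 68% | 0 | 6.3% | 6.3% | 6.3% |
| 68% | 1 | 9.4% | 7.6% | 6.2% |
| 68% | 2 | 15.9% | 10.7% | 7.0% |

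The starting values are below 10% because Fisher's test is conservative. That margin absorbs one undosed infant at either rate. With two, the nominal 10% is passed at p = 51% only toward the pessimistic end of q, and at p = 68% across the whole range from 0 to 35%. The last column shows no material rise when prognosis is the same.

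The 68% rows apply to Hypothesis 2b. Section 5.2.2 carries the same power calculation over to Hypothesis 3, but 5.3 analyses Aim 3 by Kaplan-Meier, so for Aim 3 these figures only indicate direction and rough size.

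**The case against.** The strongest reply is that few infants, perhaps none, will be enrolled and never dosed. Section 4.2.2 already excludes fluid overload, heart failure, raised creatinine and persistent hypertension after HPE. The gap from consent to dose 1 is short. An acutely ill infant is stabilised and then dosed. After a refused line, later doses are still attempted, so an infant drops out of a treated set only by missing all three. Most of the rules in 7.4 act during or after an infusion, when the infant has already received IVIG. All of this stands, and it is why the realistic range is taken as one or two infants.

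A reader might infer from the 23-29 range in 5.2.1 that the protocol expects up to six undosed infants. With six, the 51% case would give 12% (q = 35%) to 35% (q = 0). The documents do not support that as a forecast: 5.2 derives 23 from 20% loss to follow-up, and 5.2.2 uses 23 in the same sense, paired with 56 controls. Six is at most a hypothetical upper bound.

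A reader might also infer that the whole efficacy analysis is firmly treated-only. For Aim 2 the wording is mixed, the no-drop-out power uses all 29, and in a single-arm trial the phrase for treated subjects could simply label the cohort. That makes the population ambiguous for Aim 2; it does not settle it. Nor can it be said that START lacked a comparable selection step. Its placebo infants are described as having received placebo, and START's entry rules are not in the document.

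Finally, these are secondary, preliminary aims in a trial sized on feasibility and safety. That limits the stakes, but a population stated in two ways still needs to be reconciled.

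**Conclusion.** The point holds in a limited form. Section 5.2.2 and the Aim 3 text in 5.3 describe the IVIG side by receipt of drug, other text does not, and nothing assigns enrolled but undosed infants to the comparison. A treated-only set can bias the result in favour of IVIG. Under the stated assumptions on undosed infants the effect is modest: at 51% success, from 6.7% to 7-9% with one undosed and 8-12% with two; at 68%, from 6.3% to 11-16% with two. It vanishes if every infant is dosed or if missing all doses is unrelated to prognosis. The control count of 70 is the protocol's approximate figure.

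**What to change.** In 5.2.2 and in 5.3 (Aims 2 and 3), state that the efficacy group is every enrolled infant with confirmed biliary atresia, dosed or not, counted from the day of HPE, compared with all START infants assigned placebo. Keep the IVIG-treated set as a sensitivity analysis. Infants removed because histology shows another disease stay out, as 4.2 already provides.

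The cost is about one sentence in each section and no new visits. Section 4.4.4 keeps an infant in the study after a refused dose, 4.4.5 and 4.12.3 continue follow-up after IVIG is stopped, and 4.12.2 lists only withdrawn consent and loss to follow-up as reasons for removal.

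The downside is slight dilution if some infants are never dosed. If dosed infants succeed at 76.5% and undosed ones at the control rate of 51%, the IVIG rate is (28 × 76.5% + 51%) / 29 = 75.6% with one undosed and (27 × 76.5% + 2 × 51%) / 29 = 74.7% with two. Power against 70 controls falls from 82% to 80% and 77%. It falls further if the undosed do worse than controls, but that further part is the selection effect being taken out.

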# Aim 2: To obtain preliminary evidence whether IVIG therapy is associated with lower serum bilirubin concentration after HPE.

*Hypothesis 2a*: The probability of an infant having good bile drainage at 90 and 180 days after HPE (as defined by survival 90 or 180 days after HPE with both their native liver and serum total bilirubin level <1.5 mg/dL at 90 or 180 days after

HPE) will be greater in infants who are treated with IVIG compared to historical controls.

The proportions of subjects who have survived with their native liver and have bilirubin <1.5 mg/dL will be calculated at both time points. Each proportion will be compared to that of historical controls from the placebo group in the START study using Fisher's exact test. Given that previous studies have found age at HPE to be predictive of later clinical outcomes, we will perform an exploratory logistic regression analysis, including IVIG treatment (vs control) and age at HPE as covariates. Odds ratios and one-sided 90% Wald upper confidence bounds will be presented.

*Hypothesis 2b*: The probability of an infant having good bile drainage at 360 days after HPE (as defined by survival 360 days after HPE with both their native liver and serum total bilirubin level <1.5 mg/dL at 360 days after HPE) will be greater in infants who are treated with IVIG compared to historical controls.

The same methods will employed as in Hypothesis 2a.

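### Fisher's exact test uses only about 6–7% of the chosen one-sided 10% error rate in the bile-drainage comparisons; the one-sided Boschloo exact test would recover about 3.5 to 6 points of power with the same infants

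*Protocol*

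**What the plan says.** Section 5.2.2 explains the direction of testing: "A one-sided testing strategy was chosen given that we are only interested if IVIG improves the preliminary measures of efficacy". For Hypothesis 2a it takes rates of "76.5% in the IVIG group and 51% in the placebo group", assumes 20% loss in both studies, which leaves "23 subjects in the IVIG group and 56 subjects in the START placebo group", and gives the power: "there is 74% power with a one-sided Type I error rate of 10% to detect a difference of 25.5" percentage points. The method is named: "This is based on Fisher's exact test for two proportions (SAS 9.3"). Without losses, "The corresponding power for sample sizes of 29 and 70 in the IVIG and placebo groups (if there were no drop-outs) is 82" percent. A second scenario follows: "Alternatively, we have 80% power to detect a difference of 28% in this outcome", that is 79% vs 51% at 23 and 56 infants, with 88% power at 29 and 70. For Hypothesis 2b it gives 76% to 85% power for a one-third relative improvement on 68%, to about 90%.

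Section 5.3, Aim 2, fixes the same test for the 90- and 180-day analyses: "Each proportion will be compared to that of historical controls from the placebo group in the START study using Fisher's exact test". It carries the same methods over to 360 days.

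The protocol does not mention that the attained level lies below 10%, and it discusses no other exact test.

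**The concern.** Fisher's test conditions on the total number of successes. With small groups its p-value takes few distinct values for each total, so the largest rejection region with p ≤ 0.10 often has a probability well under 0.10. In this comparison the group sizes are given but the total number of successes is not, so the design does not require conditioning on it.

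The sponsor chose a lenient 10% error rate for a small trial with at most 29 infants. If the test uses only part of that rate, the rest is given up as power. The protocol says the results should help determine whether a larger trial is worth pursuing (section 2.4), so a missed signal has a cost, even in a secondary comparison.

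**Working it through.** **Inputs**, all from section 5.2.2: group sizes 23/56 and 29/70; nominal one-sided α = 0.10; Fisher's exact test; rates 76.5% vs 51%, 79% vs 51%, and 68% × 1.33 = 90.44% vs 68%.

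**Formulas.** Let x be the successes among n₁ IVIG infants and y those among n₂ controls.

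- Fisher p(x, y) = P(H ≥ x), with H hypergeometric (population n₁ + n₂, x + y successes, n₁ draws). Reject if p ≤ 0.10.
- Rejection probability for true rates π₁, π₂ = Σ Bin(x; n₁, π₁) · Bin(y; n₂, π₂), summed over all rejected tables. With π₁ = π₂ = π this is the true size at π; otherwise it is the power.
- Boschloo uses Fisher's p as its statistic, but rejects if p ≤ c, where c is the largest cut-off whose size, maximised over all π, is at most 0.10.

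**Step 1: reproduce the plan.** Enumerating every table, Fisher's power is:

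- 76.5% vs 51%: 74.3% and 82.2% (stated 74% and 82%)
- 79% vs 51%: 81.6% and 88.5% (stated 80% and 88%)
- 90.44% vs 68%: 76.4% and 85.7% (stated 76% and 85%)

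All agree within 2 points. A normal approximation would give 81.3% for the first case, so the plan did use Fisher, and its figures already include the conservatism.

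**Step 2: Fisher's true size at nominal 10%.**

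| Groups | at π = 0.51 | at π = 0.68 | maximum over π |
|---|---|---|---|
| 23/56 | 6.3% | 6.1% | 6.7% |
| 29/70 | 6.7% | 6.3% | 6.9% |

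The unused share runs from (10 − 6.9)/10 = 31% to (10 − 6.1)/10 = 39%. Because the maximum is below 7%, this does not depend on the assumed 51%.

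**Step 3: Boschloo at 10%.** The cut-off c is 0.1445 (23/56) and 0.1380 (29/70). The maximum size is 9.97% and 9.98%. Since c exceeds 0.10, every table that Fisher rejects is also rejected by Boschloo.

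| Rates | Groups | Fisher | Boschloo | Gain (points) |
|---|---|---|---|---|
| 76.5% vs 51% | 23/56 | 74.26% | 80.31% | 6.05 |
| 76.5% vs 51% | 29/70 | 82.20% | 87.05% | 4.85 |
| 79% vs 51% | 23/56 | 81.56% | 86.43% | 4.87 |
| 79% vs 51% | 29/70 | 88.47% | 92.04% | 3.57 |
| 90.44% vs 68% | 23/56 | 76.42% | 81.71% | 5.29 |
| 90.44% vs 68% | 29/70 | 85.73% | 89.25% | 3.52 |

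**Step 4: the gain in infants.** With 56 controls and 76.5% vs 51%, Fisher's power is 79.6% with 28 IVIG infants and 81.7% with 29. It therefore needs 5 to 6 more evaluable infants than 23 to reach what Boschloo gives.

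**Step 5: a borderline table.** For 16/23 vs 29/56 (70% vs 52%), Fisher's p is 0.115: not significant by Fisher, but below 0.1445 and so significant by Boschloo. One more IVIG success (17/23) gives p = 0.058, significant by both.

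**Step 6: sensitivity to non-comparable controls.** This is an assumption, not a protocol figure. Suppose IVIG does nothing, but the trial's underlying rate drifts above START's 51%. At 23/56 the false-positive rate is then 13.0% (Fisher) and 18.6% (Boschloo) for a 5-point drift, and 23.7% and 31.2% for a 10-point drift.

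**The case against.** The strongest reply is that nothing is stated wrongly. The test, its direction and its nominal level are named, the same test appears in the power calculation and the analysis, and the figures reproduce. That stands. A reader might infer that the protocol misreports its Type I error or its power; it does neither, because for an exact test 10% is an upper limit and the stated power is Fisher's own.

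A reader might also infer that the trial misses an 80% target. The protocol sets none for the 25.5-point difference: it states 74%. Its 80% belongs to the 28-point difference, where Fisher already gives 81.6%. The size of 29 rests primarily on precision for feasibility, tolerability and safety (section 5.2).

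Nor does every unconditional exact test help. Barnard's test with the plain pooled Z statistic gives 72.7% at 23/56, below Fisher. The gain has to be claimed for a named test. Whether to condition on the margins is also a long-debated choice, and Fisher is a valid, familiar answer.

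The effect on decisions should not be overstated. Section 5.3 sets no go/no-go rule on this test, and a p of 0.115 rather than one just under 0.10 should not by itself change how an unrandomised comparison is read.

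The weightiest objection is bias. Section 5.2.2 itself acknowledges the bias inherent in historical controls, and Step 6 shows that Fisher's slack acts as some cushion against it. This stands as a real downside. It applies to any fuller use of the chosen 10%, and an unstated cushion is a poor substitute for choosing a smaller α openly.

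**Conclusion.** The point holds as a cheap, optional improvement, not as an error. Fisher's attained level is about 6–7% against a chosen 10%, whatever the true control rate. One-sided Boschloo stays within the sponsor's limit, keeps every Fisher rejection, and adds 3.5 to 6 points of power in the protocol's own scenarios. The power figures rest on the protocol's assumed rates and group sizes, and on comparable controls. The 80.3% at 23/56 is only just above 80% and depends on the assumed 51% control rate. Importance is low, because the comparison is secondary, preliminary and unrandomised.

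**What to change.** In section 5.3, for Hypotheses 2a and 2b, replace Fisher's exact test with the one-sided Boschloo unconditional exact test at 10%, fixed before outcome data are seen.

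In section 5.2.2, name the same test and restate the power for 23/56 and 29/70:

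- 76.5% vs 51%: 80% and 87%
- 79% vs 51%: 86% and 92%
- 90.4% vs 68%: 82% and 89%

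Section 5.2.2 also lends the Hypothesis 2b power to Hypothesis 3, which section 5.3 analyses by Kaplan–Meier estimates. The Boschloo figures should not be carried over to it.

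The cost is one changed sentence, re-run power figures and a short program, with no extra infants, visits or data. The downsides are a less familiar test and the thinner cushion against non-comparable controls, which the text should acknowledge. If the sponsor prefers to keep Fisher for either reason, one sentence in section 5.2.2 stating that the attained level is about 6–7% would make that choice explicit.
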